11.2.1 Events of Clinical Interest

Selected non-serious and serious adverse events are also known as ECIs and must be reported to the sponsor.

ECIs must be reported following the reporting period for AEs (the initiation of study treatment through 28 days after permanent discontinuation of trial treatment) or, if they qualify as an SAE, following the reporting period for SAEs (through 90 days following cessation of trial treatment or EOS (whichever is later), or 28 days following cessation of trial treatment if the patient initiates new anti-cancer therapy). Any ECIs (as defined in this section) or follow up to an ECI that occurs in any patient **must be reported to Dynavax or its designee within 24 hours of investigator awareness of the event** (regardless of whether the investigator assesses the event as probably or possibly related to study drug). Reporting must be made by electronic media and on the Safety Report Form (regardless of whether the investigator assessed the event as serious or not serious) per SAE reporting procedures. Electronic reporting procedures can be found in the electronic data capture (EDC) data entry guidelines. Safety reporting procedures can be found in the Investigator Trial File Binder (or equivalent).

ECIs for this trial include:

- 1) An overdose of SD-101 or pembrolizumab, as defined in Section [11.2.2](#).

OR

- 2) An elevated AST or ALT lab value that is greater than or equal to 3 X the ULN and an elevated total bilirubin lab value that is greater than or equal to 2 X the ULN and, at the same time, an alkaline phosphatase lab value that is less than 2 X the ULN, as determined by way of protocol-specified laboratory testing or UNS laboratory testing.*

*Note: These criteria are based upon available regulatory guidance documents. The purpose of the criteria is to specify a threshold of abnormal hepatic tests that may require an additional evaluation for an underlying etiology. The trial site guidance for assessment and follow up of these criteria can be found in the Investigator Trial File Binder (or equivalent).

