12.1 General

This trial is designed to allow preliminary assessments of safety, biological activity, and biomarkers. No pre-specified hypothesis testing will be performed. All analyses of demographics, safety, biological activity, and biomarkers will be descriptive.

Injection-site reactions, AEs, SAEs, and abnormal laboratory values will be summarized by the proportion of patients who experience them.

ORR will be presented as the proportion of patients who achieved CR or PR. The DCR will be presented as the proportion of patients who achieved CR, PR, or stable disease.

In general, categorical data will be summarized as counts and percentages (or proportions) and continuous data will be summarized with descriptive statistics such as mean, standard deviation, median, minimum and maximum.

Final analyses will be carried out after the last participant has completed their last trial visit, the trial database has been authorized by Dynavax as complete and final, and major protocol deviations have been identified. Patient data will be reviewed for major protocol deviations by the Medical Monitor prior to database lock. A listing of patients with major protocol deviations will be provided, sorted by treatment and describing their deviations. Efficacy and safety data from each cohort may be analyzed and reported separately from other cohorts. In addition, safety data will be summarized overall and for each separate tumor indication.

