12.7 Safety Analyses

All safety data will be analyzed descriptively and will be based on the all-treated population. The most important safety parameters will be presented for all sites combined. Summary statistics will be used to describe the incidence of all injection-site reactions, AEs, SAEs, deaths, and laboratory values. DLTs occurring in Phase 1 will be summarized by dose level received and presented in both tables and listings.

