9.7 Safety Analyses

Injection related reactions, AEs, SAEs, and abnormal laboratory values will be summarized by the proportion of patients who experience them.

All patients in the safety population will be used in the safety analyses. Safety analyses will be summarized by dose or analysis group.

The treatment-emergent period is defined in [Section 7.1](#).

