9.7.4 Laboratory Assessments

Laboratory test results for neutrophils, lymphocytes, and platelets and their change from baseline will be summarized by tumor type and scheduled visit.

Laboratory data listings will not be produced as clinically significant abnormal laboratory findings are included in AE data.

Anti-dsDNA antibodies (not implemented) and anti-SD-101 antibodies results will be provided as part of the Annex 1 analysis.

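### SAP 9.7.4 does not specify the abnormal-laboratory-value summary that SAP 9.7 and Protocol 12.1 and 12.7 promise, so liver, renal, glucose and thyroid abnormalities would be reported only through recorded AEs

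*SAP*

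**What the plan says.** The general commitment appears three times. SAP Section 9.7: "Injection related reactions, AEs, SAEs, and abnormal laboratory values will be summarized by the proportion of patients who experience them". Protocol Section 12.1: "Injection-site reactions, AEs, SAEs, and abnormal laboratory values will be summarized by the proportion of patients who experience them". Protocol Section 12.7: "Summary statistics will be used to describe the incidence of all injection-site reactions, AEs, SAEs, deaths, and laboratory values". SAP Section 9.7 also fixes the grouping: "Safety analyses will be summarized by dose or analysis group".

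The implementing section, SAP 9.7.4, reads: "Laboratory test results for neutrophils, lymphocytes, and platelets and their change from baseline will be summarized by tumor type and scheduled visit". It then states: "Laboratory data listings will not be produced as clinically significant abnormal laboratory findings are included in AE data". Its only other content sends anti-SD-101 antibody results to Annex 1 and marks anti-dsDNA antibodies as not implemented.

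Protocol Section 11.2.1 defines two events of clinical interest (ECIs). One is overdose. The other is a liver signal made of three laboratory conditions. The first is "An elevated AST or ALT lab value that is greater than or equal to 3 X the ULN"; it is combined with total bilirubin of at least 2 times ULN and alkaline phosphatase (ALP) below 2 times ULN at the same time.

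**The concern.** The parent section promises one kind of output and the implementing section specifies another. A programmer working from 9.7.4 would produce by-visit means for three blood counts and nothing for chemistry or thyroid function.

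The omitted analytes matter in this trial. Protocol Section 9.0 singles out immune-related effects on organs that include the liver and the endocrine system. Table 7-1 covers transaminase and bilirubin elevation, type 1 diabetes and hyperglycemia, thyroid disorders and nephritis. These are often seen first in laboratory results. If they are reported only as AEs, the rate depends on which findings investigators judged clinically significant. The report would then contain no laboratory-based figure to set beside the AE rate.

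**Working it through.** No plan figure needs reproducing and no formula applies. The check compares what is collected and promised with what is specified.

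1. Panels in Protocol Section 10.3.6 against the summaries named in SAP 9.7.4:

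| Panel | Tests collected | Summarized in 9.7.4 |
|---|---|---|
| Chemistry (includes AST, ALT, bilirubin, ALP, creatinine, glucose) | 14 | 0 |
| Thyroid (free T3, free T4, TSH) | 3 | 0 |
| Coagulation (PT, aPTT) | 2 | 0 |
| Hematology | hemoglobin, hematocrit, white cells with differential, platelets | platelets and two differential components |

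Outside hematology the count is 0 of 14 + 3 + 2 = 19 tests.

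2. Type of summary. SAP 9.7 and Protocol 12.1 call for the proportion of patients with abnormal values. SAP 9.7.4 gives values and change from baseline. So the promised proportion is not specified even for the three counts. The footnotes to Protocol Appendices 1 to 4 say laboratory measurements are graded by CTCAE 4.03, but no SAP output reports a laboratory grade.

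3. Grouping. SAP 9.7 requires dose or analysis group. SAP 9.7.4 uses tumor type, so the three counts would not be shown by SD-101 dose.

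4. Is it a declared departure? SAP Section 1.0 says objectives that are not evaluated will be marked as not implemented. SAP Section 7.1 says openly that the treatment-emergent periods differ from the protocol. In 9.7.4 only anti-dsDNA antibodies carry the mark. Vital signs, physical examinations and ECGs all keep listings (SAP 9.7.5 to 9.7.7).

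5. The stated reason. SAP 9.7.4 relies on AE data. Protocol Section 11.2 counts an abnormal laboratory finding as an AE only if it is clinically significant. Abnormal values below that judgment reach no output described in the SAP.

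6. The liver ECI. The SAP does not mention ECIs, and the table list in SAP 9.7.3 has no ECI output. A reported case would appear under its preferred terms but would not be identified as meeting the joint criteria. A case that met the criteria but was not reported could not be found from any described output.

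7. Are there data to summarize? Appendix 1 schedules chemistry, coagulation and thyroid tests repeatedly in Phase 1. Appendix 4 still marks on-treatment chemistry for Cohorts 5 to 8, although its footnote refers to local standard of care. Appendices 2 to 4 keep chemistry, hematology and thyroid tests at the end-of-study (EOS) visit.

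**The case against.** The strongest reply is that these events are not lost. Protocol Section 11.2.1 describes ECIs as selected adverse events with mandatory 24-hour reporting. SAP 9.7.3 tabulates TEAEs by system organ class, preferred term, severity and relationship. It adds a table of immune-related TEAEs and lists every TEAE. In Phase 1, clinically significant Grade 3 laboratory AEs can also count as DLTs. This stands, and it limits the consequence.

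A reader might infer that a patient meeting the liver criteria could be missing from every table and listing. The documents support that only if the site also failed a mandatory report. A reader might also infer that the AE rationale breaks down for the liver ECI because an ECI stands with or without an AE. The protocol applies that wording to overdose only (Synopsis and Section 11.2.2), not to the liver criteria.

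Second, SAP 9.7.4 does not say that only three analytes will be summarized, and it bars listings rather than tables. The commitment in SAP 9.7 has not been withdrawn, and the table list sits in a separate document (SAP Section 12.0) that was not available. So the promised table may exist there. This stands as a caveat, but the SAP itself specifies no such table.

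Third, Amendment 9 reduced laboratory collection, and Protocol Section 12.0 now limits Phase 2 to selected analyses. That does not remove the point. The Synopsis carries a similar limitation and still names abnormal laboratory values among the analyses. Section 12.0 also keeps the Phase 1 analyses as detailed there.

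**Conclusion.** The point holds as an internal contradiction. SAP 9.7.4 does not deliver the abnormal-value summary promised in SAP 9.7 and Protocol 12.1 and 12.7, and it bars listings without declaring a departure. Followed as written, 0 of 19 chemistry, thyroid and coagulation tests has a laboratory summary. There is no laboratory-based incidence or grade for liver, renal, glucose or thyroid abnormalities. No output identifies patients meeting the Section 11.2.1 liver criteria or checks that such cases were reported.

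It would go too far to infer that the safety and tolerability objective cannot be answered for these organs. There is an AE-based answer. It depends on investigator recording and cannot be checked against laboratory data in the planned outputs.

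The conclusion assumes that 9.7.4 governs what is programmed and that the separate table list does not already contain the missing table.

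**What to change.** Amend SAP 9.7.4 to specify the summary promised in 9.7:

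- **Abnormal-value table.** Give the proportion of patients with abnormal post-baseline values by dose or analysis group. Use worst CTCAE grade, or low/normal/high where no grade applies. Cover hematology, AST, ALT, bilirubin, ALP, creatinine, glucose and thyroid tests. Other formats would also meet the protocol wording; worst grade fits the grading already required by the appendix footnotes.
- **Data.** Use all laboratory data in the database, including EOS results, with no cut-off at Amendment 9. Add a note that Phase 2 on-treatment data are limited after that amendment, because results from local standard-of-care testing need not be entered on the CRF (Protocol Section 10.0).
- **Liver criteria.** Add a count and listing of patients meeting the joint AST/ALT, bilirubin and ALP criteria of Protocol Section 11.2.1. State which samples count as simultaneous, and compare the list with the reported ECIs.
- **Listings.** Replace the blanket bar with wording that permits this listing. Listings of every analyte are not needed.

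If the sponsor prefers AE-only reporting, the SAP should say that this departs from Protocol 12.1 and 12.7, and why.

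The cost is a small number of additional standard outputs. That assumes the collected results and their reference ranges are in the database, which the documents do not confirm. No new data collection is required.

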9.7.5 Vital Signs

Vital sign data will be provided in a data listing.

9.7.6 Physical Examinations

Individual physical examination data with abnormal findings flagged will be provided in data lists.

9.7.7 Electrocardiograms

ECG data with abnormal findings flagged will be provided in a data listing.

9.8 Pharmacodynamic Analyses

Plan for pharmacodynamic analyses is included in Annex 1 of this SAP.

9.9 Other Analyses

No other analyses are planned.

9.10 Interim Analysis

No interim analysis is planned for this protocol. Safety will be monitored on a regular basis.

9.11 Reporting Output

All outputs will be produced using SAS[®] version 9.3 or later. The REPORT procedure will be used to produce all tables and listings whenever possible. The SGPLOT procedure will be used to produce all figures whenever possible. All statistical appendices (supportive SAS output) will be output directly from the appropriate SAS procedure.

Post-text tables, listings, and statistical appendices will be produced as RTF files using output delivery system (ODS) and Times New Roman or a similar font size 8 or larger. Data

will be presented in RTF tables with data in individual cells. Figures will be produced as RTF files using ODS and simplex font. For all outputs, the page numbering will be applied to ensure that when the RTF files are combined, the page numbering remains fixed.

All tables, listings and statistical appendices will be produced to landscape orientation and will be incorporated into a Word 2010 or later document (margins: top 1.5”, left, right and bottom 1”) using 8pt font or larger.

Dose and analysis groups for tables and figures will be as follows:

- for Phase 1: Dose Escalation Phase objectives
 - 1 mg, 2 mg, 4 mg, 8 mg
- for Phase 2: Expansion Phase objectives
 - MEL/Naive (metastatic melanoma patients anti-PD-1/L1 therapy naïve)
 - 2mg, 8mg
 - MEL/Experienced (metastatic melanoma patients progressed on anti-PD-1/L1 therapy)
 - 2mg, 8mg
 - HNSCC/Naive (HNSCC patients anti-PD-1/L1 therapy naïve)
 - 2mg, 8mg
 - HNSCC/Experienced (HNSCC patients progressed on anti-PD-1/L1 therapy)
 - 2mg, 8mg

10.0 REVISION HISTORY

Version	Date	Author	Comments/Rationale for Revision
1.0	04NOV2019	[name]	New Document

11.0 REFERENCES

12.0 LIST OF TABLES

List of tables will be provided in a separate Table of Contents of Tables, Figures and Listings document.

Approved

13.0 LIST OF FIGURES

List of figures will be provided in a separate Table of Contents of Tables, Figures and Listings document.

Approved

14.0 LIST OF PATIENT DATA LISTINGS

List of listings will be provided in a separate Table of Contents of Tables, Figures and Listings document.

Approved

APPENDIX 1 RECIST V1.1**Response Definition**

Assessments will use RECIST 1.1 guidelines, which are included in the Study Reference Manual, and study specific modification of the RECIST 1.1 guidelines referred to as immune related RECIST 1.1 (irRECIST 1.1).

RECIST 1.1

Baseline selection of lesions

All lesions are measured by long axis and short axis (perpendicular to the long axis). At baseline, all tumor lesions are identified as either target lesions or non-target lesions and will be evaluated at baseline and every post baseline imaging timepoint.

Target lesions: Minimal size of 1.0 cm by long axis unless a lymph node which must be a minimal size of 1.5 cm by short axis. Superficial lesions must measure at least 10 mm in long diameter and be measurable by calipers to qualify as target lesions. Maximum target lesions are 5 with a maximum of 2 lesions per organ representative of all involved organs.

Non-target lesions: Radiographically visible but do not meet size qualification of target lesions. Lymph nodes must measure at least 1.0 cm by short diameter to qualify as non-target lesions (if smaller considered non-pathologic). Excess target lesions (> 5 overall or 2 per organ) are followed as non-target lesions.

Baseline measurement of lesions

At baseline, the sum of the long diameters of all target lesions (5 lesions total with maximum of 2 lesions per organ representative of all involved organs), is calculated. The sum is referred to as the sum of diameters (SOD) for the baseline timepoint. All other lesions should be identified as non-target lesions and be recorded at baseline.

Postbaseline radiographic response assessment

At each post baseline imaging timepoint, the long axis diameter of all target lesions are measured and recorded. A response of the target lesions is assessed by determination of the overall SOD of the lesions (SOD for that imaging timepoint). A response for each baseline non-target lesion is determined and recorded. The presence of any new lesions are recorded (of note a lymph node must measure at least 1.0 cm by short axis diameter to qualify as a pathologic lesion).

Target lesion response

Complete response (CR): disappearance of all target lesions. Any pathological lymph nodes (whether target or non-target) must have reduction in short axis to < 10 mm.

Partial response (PR): At least a 30% decrease in the sum of diameters of target lesions, taking as reference the baseline sum of diameters.

Progressive disease (PD): At least 20% increase in the sum of diameters of target lesions, taking as reference the smallest prior sum of diameters in the trial (this includes the baseline sum if that is the smallest in the trial). In addition to the relative increase of 20%, the sum must also demonstrate an absolute increase of least 5 mm.

Stable disease (SD): Neither sufficient shrinkage to qualify for PR nor sufficient increase to qualify for PD, taking as reference the smallest sum of diameters while in the trial.

Non-target lesion response assessment

Complete response (CR): Disappearance of all non-target lesions and normalization of tumor marker level. All lymph nodes must be non-pathological in size (<10 mm short axis).

Non-CR/Non-PD: Persistence of 1 or more non-target lesion(s) and/or maintenance of tumor marker level above the normal limits.

Progressive disease (PD): Unequivocal progression of existing non-target lesions. (Note: the appearance of 1 or more new lesions is also considered progression).

New lesion assessment

At each post baseline imaging timepoint, an evaluation of the presence of new lesions (yes/no) is made. The lesions are recorded as new lesions and not target or non-target lesions.

Lymph nodes must be a new lesion and measure at least 10 cm by short diameter to qualify as a new lesion overall response assessment.

A lesion identified on a follow-up study in an anatomical location that was not scanned at baseline is considered a new lesion.

Overall response assessment

Overall response assessment is based on target lesion response, non-target lesion response and new lesions and is listed in Figure 1 below.

Figure 1: Overall Response Definitions Using RECIST 1.1

Target Lesions	Non-target Lesions	New Lesions	Overall Response
CR	CR	No	CR
CR	Non-CR/non-PD	No	PR
CR	Not evaluated	No	PR

PR	Non-PD or not all evaluated	No	PR
SD	Non-PD or not all evaluated	No	SD
Not all evaluated	Non-PD	No	NE
PD	Any	Yes or No	PD
Any	PD	Yes or No	PD
Any	Any	Yes	PD

CR = complete response; NE = not evaluable; PD = progressive disease; PR = partial response; SD = stable disease.

Approved

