At each post-baseline imaging time point, the long axis diameter of all target lesions is measured and recorded. A response of the target lesions is assessed by determination of the overall SOD of the lesions (SOD for that imaging time point). A response for each baseline non-target lesion is determined and recorded. The presence of any new lesions is recorded (of note a lymph node must measure at least 1.0 cm by short axis diameter to qualify as a pathologic lesion).

Target lesion response

Complete response (CR): disappearance of all target lesions. Any pathological lymph nodes (whether target or non-target) must have reduction in short axis to < 10 mm.

Partial response (PR): At least a 30% decrease in the SOD of target lesions, taking as reference the baseline SOD.

Progressive disease (PD): At least 20% increase in the SOD of target lesions, taking as reference the smallest prior SOD in the trial (this includes the baseline sum if that is the smallest in the trial). In addition to the relative increase of 20%, the sum must also demonstrate an absolute increase of least 5 mm.

Stable disease (SD): Neither sufficient shrinkage to qualify for PR nor sufficient increase to qualify for PD, taking as reference the smallest SOD while in the trial.

Non-target lesion response assessment

Complete response (CR): Disappearance of all non-target lesions and normalization of tumor marker level. All lymph nodes must be non-pathological in size (<10 mm short axis).

Non-CR/Non-PD: Persistence of 1 or more non-target lesion(s) and/or maintenance of tumor marker level above the normal limits.

Progressive disease (PD): Unequivocal progression of existing non-target lesions. (Note: the appearance of 1 or more new lesions is also considered progression).

New lesion assessment

At each post-baseline imaging time point, an evaluation of the presence of new lesions (yes/no) is made. The lesions are recorded as new lesions and not target or non-target lesions.

Lymph nodes must be a new lesion and measure at least 10 mm by short diameter to qualify as a new lesion overall response assessment.

A lesion identified on a follow-up study in an anatomical location that was not scanned at baseline is considered a new lesion.

Overall response assessment

Overall response assessment is based on target lesion response, non-target lesion response and new lesions and is listed in [Table 1](#) below.

Table 1: Overall Response Definitions Using RECIST v1.1

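### Nodal target lesions qualify and reach CR by short axis but enter the sum of diameters by long axis, so PR, SD and PD can be misclassified in patients with nodal targets

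*SAP*

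**What the plan says.** SAP Appendix 1 sets the size rule for a target lesion as "Minimal size of 1.0 cm by long axis unless a lymph node which must be a minimal size of 1.5 cm by short axis". Its CR rule adds a nodal condition: "Any pathological lymph nodes (whether target or non-target) must have reduction in short axis to < 10 mm". A node also has to reach 1.0 cm in short axis to count as pathologic or as a non-target lesion.

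The sum of diameters is built differently. The appendix takes "At baseline, the sum of the long diameters of all target lesions", with no exception for nodes. At follow-up it says that "the long axis diameter of all target lesions are measured and recorded"; Protocol Appendix 6 matches, with "the long axis diameter of all target lesions is measured and recorded". PR is then "At least a 30% decrease in the sum of diameters of target lesions, taking as reference the baseline sum of diameters". PD needs an increase of at least 20% over the smallest sum and at least 5 mm. SD is what lies between.

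Under the heading on baseline selection, the appendix also says "All lesions are measured by long axis and short axis (perpendicular to the long axis". It refers to the RECIST 1.1 guideline in the Study Reference Manual, which was not available for this review.

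ORR per RECIST v1.1 is the Phase 2 primary endpoint (SAP 4.0). SAP 9.6 has the investigator determine ORR and DCR, and asks for both by injected, non-injected and all target lesions.

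**The concern.** One lesion is judged on two different axes within one response algorithm. A node becomes a target and is declared normal by its short axis, yet its shrinkage or growth between those points is read from its long axis. If the two do not move together, the sum can miss a partial response, or call or miss progression.

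The categories feed ORR, DCR, duration of response and PFS. The documents expect nodes among the lesions that matter most. Lesion A must be a RECIST target (Protocol 6.2.2.2 and 6.2.2.3) and is biopsied, and Protocol 10.1.2 gives peripheral lymph nodes as an example of a suitable biopsy site. An injected node may therefore be the main target lesion.

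**Working it through.** There is no stated figure to reproduce, because the point concerns a measurement rule. The check applies the appendix's own thresholds to assumed nodal sizes, once with the node entered by long axis (as written) and once by short axis (as its eligibility and CR rules imply).

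Inputs from SAP Appendix 1: PR is a fall of at least 30% from the baseline sum; PD is a rise of at least 20% and at least 5 mm from the smallest sum; the nodal CR condition is a short axis below 10 mm.

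Assumptions: the sizes below; smallest prior sum equal to baseline; no new lesions and no non-target progression.

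Formula: percentage change = (follow-up sum − baseline sum) / baseline sum.

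| Case (short × long, mm) | Node by long axis | Node by short axis |
|---|---|---|
| A. Node 15 × 25 to 10 × 20 | (20 − 25)/25 = −20.0%: SD | (10 − 15)/15 = −33.3%: PR |
| B. Node 16 × 32 to 9 × 28, plus non-nodal lesion 30 to 22 | (50 − 62)/62 = −19.4%: SD | (31 − 46)/46 = −32.6%: PR |
| C. Node 16 × 20 to 16 × 25 | (25 − 20)/20 = +25%, +5 mm: PD thresholds met | 0%: SD |
| D. Node 20 × 30 to 25 × 32 | (32 − 30)/30 = +6.7%, +2 mm: SD | (25 − 20)/20 = +25%, +5 mm: PD thresholds met |
| E. Node 18 × 30 to 12 × 20 | (20 − 30)/30 = −33.3%: PR | (12 − 18)/18 = −33.3%: PR |

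The separate CR rule rescues neither A nor B. In A the short axis is 10 mm, which is not below 10. In B the node has normalized but the non-nodal lesion persists. Cases C and D show that the discrepancy runs in both directions.

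Case E shows the limit. If a single node shrinks in proportion, the percentage is the same on both axes and the axis does not matter. A grid of 400 proportional changes (baseline short axis 15 to 30 mm, long/short ratio 1 to 2, follow-up 30% to 150% of baseline) gave 9 disagreements. Because the percentages are identical in that grid, only the 5 mm part of the PD rule can produce a difference. The grid excludes disproportionate change by construction, so it is not an estimate of how often patients would be affected.

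**The case against.** The strongest reply is that overall response is the investigator's call (SAP 4.0 and 9.6), made under the RECIST 1.1 guideline that the appendix cites. The SAP describes no program that derives overall response from the sum. Misclassification then arises only where investigators followed the written summary literally, or where a response is derived from measurements. That stands, and it shapes the fix. It does not settle the matter. The appendix cites the guideline and then sets out explicit rules of its own. SAP 4.0 ties investigator evaluation to the overall response assessment, which leaves the source of the injected and non-injected responses unstated.

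Three stronger readings are tempting and are not supported:

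- **That the long axis is the only axis recorded, so nodal CR cannot be derived.** This is an inference from silence. Nothing bars recording the short axis, and the CR and new-node rules presuppose a follow-up reading. What can be said is that the written recording rule does not guarantee that nodal CR can be verified from the database.
- **That a sole nodal target falling to 9 mm in short axis scores SD because its long axis barely moved.** The CR rule has its own nodal test, independent of the sum, and such a node meets it.
- **That one scan like case C makes a PFS event.** SAP 9.6 requires confirmation at least 4 weeks later, with both scans meeting PD criteria, unless the patient is clinically unstable. PFS in SAP 9.6.6 uses confirmed PD. A transient change in node length would not count in a stable patient; a lasting one could.

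It is also true that Protocol Appendix 6 has been for information only since Amendment 9, that Phase 2 response data are no longer collected, and that the analyses are descriptive. SAP Appendix 1 carries no information-only note, however, and Protocol 8.2.1.1 allows ORR and DCR to be analyzed on data collected before that amendment.

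**Conclusion.** The inconsistency is in the SAP's operative response definition and should be corrected. With the documents' own thresholds, the choice of axis can move a patient with a nodal target between SD and PR, or between SD and PD, in either direction. It does so when the axes change disproportionately, when the node's weight against other lesions matters, or, under proportional growth, through the 5 mm rule.

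A reader might go further and conclude that PR, SD and PD are wrong in nodal disease generally, or that the error differs by tumor type. The documents support neither. Many nodal changes give the same category on both axes, and no figure is given for how many patients have nodal targets, in either tumor type, or for how their axes changed. The effect on ORR, DCR, duration of response or PFS therefore cannot be computed. The examples rest on assumed sizes and show only that a change of category is possible. The case report form fields were also not available, so whether the short axis was captured after baseline remains open.

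**What to change.** In SAP Appendix 1:

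- Define the sum of diameters as long axis for non-nodal and short axis for nodal target lesions, at baseline and at follow-up.
- Apply that sum wherever response is derived from measurements, including any injected or non-injected subset response.
- Keep the investigator-recorded overall response as the primary source for ORR, and state for each response whether it is investigator-reported or derived.
- Flag patients with nodal targets. Where post-baseline short axis was captured, report a sensitivity ORR and DCR with the corrected sum. Do not mix re-derived and investigator-reported responses within the primary endpoint.
- Align the reference text in Protocol Appendix 6. This cannot change what was collected, but it removes the conflict.

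The cost is SAP wording, a check of which axes were captured, and one added sensitivity derivation. The downside is that post-baseline short-axis values may be missing for some patients, so the sensitivity analysis may cover only part of the nodal group.
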